#### **4.3.8 Exploratory Analysis:**

Glucose levels within range, >180 mg/dl, >250 mg/dl will be measured and analyzed as the mean incremental area under the curve (AUC(0-5hrs) in minutes\*mg/dL) during exercise.

Time and Proportional time (percentage within range, >180 mg/dl, >250 mg/dl) will be calculated and treatment difference will be calculated using ANOVA/Kruskal–Wallis test, based on whether the data is normally distributed or not respectively.

Generally, unless otherwise stated, the mean incidence rates will be compared using the T tests/ ANOVA or ANCOVA models using treatment arm at Outpatient phase, treatment sequence, obtained by combining the received treatments at CRC and Outpatient phase, sex as factors with, if applicable, age and weight as covariates.

Glucose tablet utilization during exercise, food (carbohydrate) intake pre/post exercise, number of exercise sessions completed across the 3 outpatient treatment arms , number of minutes exercised per week, number of calories burned per exercise sessions, number of steps, distance

covered, heart rate, floors climbed and change from Baseline in body weight will be compared for the treatment arms using T tests/ ANOVA at CRC/ Outpatient phase.

Incidence of overnight hypoglycemia will be compared for the treatment arms using Chi-Square/Fisher's exact tests at CRC/ Outpatient phase.

HbA1c data will be summarized using descriptive statistics (n, mean, SD, median, min, and max) for each scheduled study assessment, as well as change from baseline, will be summarized using ITT and PP Population.

Example of SAS syntax code that can be used for exploratory analysis is provided in APPENDIX 3.

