#### 4.6.3 APPENDIX 3. Example of SAS syntax code for exploratory analysis.

The ANCOVA model can be analyzed using the following SAS code example:

```
PROC MIXED DATA=XXXX;
  CLASS SUBJECT TREATMENT trtSEQ sex;
  MODEL &par= TREATMENT trtSEQ sex age weight/DDFM=SATTERTH;
  RANDOM SUBJECT (SEQ);
  REPEATED / GROUP=TREATMENT SUB=SUBJECT R;
  LSMEANS TREATMENT / CL;
  LSMESTIMATE TREATMENT 'Treatment A vs. Treatment B' 1 1 0 /
  CL ALPHA=0.025 E LOWER;
RUN;
```

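### The optional exploratory ANCOVA in SAP 4.3.8 cannot estimate glucagon versus placebo, its example contrast is a one-sided sum, and letters A and B are reversed between protocol and SAP

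*SAP*

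**What the plan says.** SAP 4.3.8 says that, unless stated otherwise, mean incidence rates are compared by "T tests/ ANOVA or ANCOVA models". The factors are "treatment arm at Outpatient phase, treatment sequence, obtained by combining the received treatments at CRC and Outpatient phase, sex as factors", with age and weight as covariates where applicable. It refers to Appendix 3, introduced as "Example of SAS syntax code that can be used for exploratory analysis". The relevant lines there are:

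- "CLASS SUBJECT TREATMENT trtSEQ sex"
- "MODEL &par= TREATMENT trtSEQ sex age weight/DDFM=SATTERTH"
- "RANDOM SUBJECT (SEQ" (the parenthesis closes straight after SEQ)
- "LSMESTIMATE TREATMENT 'Treatment A vs. Treatment B' 1 1 0", with the options "CL ALPHA=0.025 E LOWER"

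Other sections bear on these lines:

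- SAP 4.3.7 specifies an ANCOVA for the questionnaires in which the sequence term is the CRC-phase sequence alone.
- SAP 4.3.6 makes all significance testing two-sided at 0.05.
- Protocol 12.1 analyses the CRC data separately from the outpatient data.
- Protocol 2.2 gives letter A to placebo with pump reduction and B to glucagon with pump reduction. SAP 2.3 gives A to glucagon and B to placebo, both with pump reduction. C is glucagon without pump reduction in both.
- SAP 4.4 records no changes from the protocol, and the SAP introduction says that the SAP prevails.

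**The concern.** The model contains the outpatient arm and also a sequence factor built partly from the outpatient treatment. Once sequence is in the model, little or nothing is left for arm to explain. The comparison that is lost is glucagon against placebo, which is the reason for fitting the model.

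The example contrast has a different fault. Its label promises a difference, but its coefficients add the two means. It is also lower-tailed at 0.025, whereas the SAP text calls for two-sided testing. In addition, the RANDOM line uses a variable, SEQ, that is not in the CLASS or MODEL statement; the declared name is trtSEQ.

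The faults interact. Under the fullest reading of sequence the program fails visibly. Under a narrower reading, or once sequence alone is repaired, the 1 1 0 contrast runs and prints a plausible number under the wrong label. Once the contrast is repaired as well, its sign depends on which document's letters are used.

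**Working it through.** The plan gives no figure for this point, so there is nothing to reproduce. The check is on the rank of the design matrix.

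**Inputs.** Three outpatient arms at 1:1:1 and two CRC orders (protocol 8.5). 48 subjects randomized, or 3 × 14 = 42 completers (SAP 1.3). Fixed effects from Appendix 3: arm, sequence, sex, age, weight. Assumptions: one outpatient row per subject, equal arms, and CRC order balanced within arm. Letters below follow SAP 2.3.

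**Step 1: degrees of freedom for arm.** These equal the rank with arm minus the rank without it. Without arm, rank = 1 (intercept) + (sequence levels − 1) + 1 (sex) + 1 (age) + 1 (weight).

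| Sequence defined as | Rank without arm | Rank with arm | Arm df | Residual df, N = 48 / 42 |
|---|---|---|---|---|
| CRC order × arm, 6 levels | 1+5+3 = 9 | 9 | 0 | 39 / 33 |
| CRC order × drug, 4 levels | 1+3+3 = 7 | 8 | 1 | 40 / 34 |
| CRC order only, 2 levels | 1+1+3 = 5 | 7 | 2 | 41 / 35 |

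With six levels, each arm indicator is the sum of two sequence indicators, so arm adds nothing. A three-level combination that ignores order gives the same result (rank 6 with and without arm). With four levels, the indicator for arm B (placebo) is the sum of the two placebo sequences. Only A versus C remains, which is glucagon with versus without pump reduction.

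**Step 2: what can be estimated.** A contrast is estimable if adding it as a row leaves the rank unchanged. LS-means weight the sequence levels equally.

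| Quantity | 6 levels | 4 levels | CRC order only |
|---|---|---|---|
| A − B (glucagon minus placebo, both with reduction) | no | no | yes |
| C − B (glucagon without reduction, minus placebo) | no | no | yes |
| A − C | no | yes | yes |
| A + B (coefficients 1 1 0) | no | yes | yes |

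**Step 3: why the sum survives with four levels.** Let s1, s2 be the glucagon sequences and s3, s4 the placebo sequences, with other terms omitted.

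- LSM A + LSM B = 2μ + a_A + a_B + (s1+s2+s3+s4)/2.
- The mean of arm A over its two sequences is μ + a_A + (s1+s2)/2. The mean of arm B over its two is μ + a_B + (s3+s4)/2. Their sum is the same expression, so it is estimable.
- Their difference is a_A − a_B + (s1+s2−s3−s4)/2, which cannot be separated into arm and sequence.

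**Step 4: the contrast.** The coefficients sum to 1 + 1 + 0 = 2, where a difference needs 0. If both arms have mean m, the estimate is 2m; at m = 10 it is 20 and the correct answer is 0. The incidence rate cannot be negative whichever way the ratio in 4.3.6 is taken. A lower-tailed test of the sum against 0 therefore says nothing about A versus B.

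**Step 5: the letters.** Swapping A and B leaves 1 1 0 unchanged but reverses the sign of 1 −1 0. If the contrast were corrected and LOWER kept, it would look for a lower rate with glucagon under the SAP letters and a lower rate with placebo under the protocol letters.

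**The case against.** **Reach.** The ANCOVA may govern no listed endpoint. The only incidence item among the exploratory endpoints is overnight hypoglycemia, which 4.3.8 assigns to chi-square or Fisher's exact tests. The primary rate has its own ANOVA in 4.3.6, and no table title in SAP 5.1 names an ANCOVA. This stands, and it is the main reason for the low grade. The model is nevertheless written into 4.3.8 for mean incidence rates, the measure that 4.3.6 uses, and the tables analysing incidence of hypoglycemia name no method.

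**Data layout.** The RANDOM and REPEATED lines suggest several rows per subject. If CRC and outpatient rows were stacked so that treatment varied within subject, A − B would be estimable even with six sequence levels. That is correct. However, 4.3.8 names the outpatient arm, which is constant within subject, and protocol 12.1 separates the phases, so this layout does not fit the text.

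**Template code.** Appendix 3 is an example with placeholder names, and trtSEQ is not defined there. The SEQ mismatch may be no more than a naming slip, and the 1 1 0 may have lost a minus sign in typing or in text extraction. Neither can be excluded, though minus signs elsewhere in the SAP code are intact. The aliasing does not depend on the code, because it is in the wording of 4.3.8.

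**Sidedness.** A one-sided 0.025 test has the same lower-tail threshold as a two-sided 0.05 test. With the contrast corrected, conclusions would differ only for an effect in the other direction. This stands, but the conflict with 4.3.6 remains.

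**Letters.** SAP 2.3 spells out each treatment and the SAP prevails. The risk remains only if another study file, such as the randomization list, uses the protocol letters; that file is not among the documents.

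**Conclusion.** The concern holds and is minor. With one outpatient row per subject, any sequence factor that includes the outpatient treatment makes glucagon versus placebo non-estimable. Arm keeps 0 df with six levels or 1 df with four, where CRC order alone would leave 2; the result is the same at 48 and 42 subjects. As printed, the example contrast is a one-sided sum that equals 2m when both arms have mean m. The undeclared SEQ and the reversed letters are further slips in the text and need to be reconciled.

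The primary ANOVA has no sequence term, and the questionnaire ANCOVA in 4.3.7 uses CRC sequence only, so neither is affected by the aliasing. The sample size does not change. The rank results assume that every combination of CRC order and arm is filled, as in the balanced layout used here.

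**What to change.** - In SAP 4.3.8, define sequence as CRC order only (glucagon then placebo, or placebo then glucagon), in line with 4.3.7.
- In Appendix 3, code each glucagon arm minus placebo. With the SAP letters these are 1 −1 0 for A − B and 0 −1 1 for C − B. Use two-sided alpha 0.05 and remove LOWER.
- Make the RANDOM term use the declared sequence variable, or drop it for endpoints with one row per subject.
- Use one set of A/B/C letters in both documents, note the change in SAP 4.4, and check the letters against the randomization list before unblinding.

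The first two changes should be made together, because correcting the sequence alone leaves a contrast that runs and is mislabelled. The cost is limited to SAP text, example code and labels, with no new data and no burden on subjects.

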#### 1.3.1 Randomization and Blinding

The study statistician will create the randomization schedule for the study. The randomization assignment for the subject will be conducted once at the time of enrollment and confirmation of eligibility. The CRC assignments will be by random assignment during the first session to either Glucagon RTU or Placebo. At the second session, the subject will be crossed over to the other treatment assignment. At the completion of the CRC visits, the subject will then have his/her treatment assignment applied for the parallel group study.

The cross-over study is blinded to the extent possible since all subjects will receive both Glucagon RTU and placebo. All staff, subjects and study team members will know that the subject will receive both study treatments during the CRC sessions. During the outpatient study, two of the treatments will be blinded to the study staff, subjects and Sponsor. One arm of the study will be open label. It is imperative for the study staff to remain blinded to treatment assignment prior to randomization and during the study treatment periods as not to bias the outcome.

Glucagon RTU and Placebo will be prepared and administered so that the two will be indistinguishable.

Blinding of study treatment is critical to the integrity of this clinical trial. It is expected that in the majority of cases, AEs can be properly managed without the need for unblinding. However, in the event of a medical emergency in which knowledge of an individual subject's treatment

assignment is considered critical to the subject's management, the treating physician may unblind the treatment assignment. The investigator should contact the responsible Medical Director to discuss the subject and circumstances requiring the unblinding. The blind will be broken only for the specific subject under discussion. The Sponsor will remain blinded to the treatment assignment. Every effort will be made to restrict knowledge of the treatment assignment to the investigator only.

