#### Secondary Endpoints:

1. Interstitial glucose (IG) levels below target range, measured by unblinded CGM (inpatient and outpatient), defined as both time (in minutes) and mean decremental area over the curve (AOC (0-300 min) in minutes\*mg/dL) during exercise:
  - Below range, as defined by  $IG \leq 70 \text{ mg/dL} (\leq 3.89 \text{ mmol/L})$

- Below range, as defined by IG between 54 to 70 mg/dL (3–3.89 mmol/L)
- Below range, as defined by IG < 54 mg/dL (<3 mmol/L)
- Proportional time (percentage time within hypoglycemia IG  $\leq$  70 mg/dL (3.89 mmol/L) and clinically significant hypoglycemia IG < 54 mg/dL (3mmol/L)).

2. Insulin utilization as reported by subject at baseline, and weeks 4, 8 and 12 in the outpatient setting.
3. Change from Baseline to the end of the Outpatient Phase in PROs: Barriers to Physical Activity in Diabetes (Type 1) (BAPAD-1), Hypoglycemia Fear Survey (HFS-II), and Hypoglycemic Confidence Scale (HCS).

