#### **4.3.7 Secondary Endpoint Analysis:**

Glucose levels below target range will be measured and analyzed as the mean decremental area over the curve (AOC(0-5hrs) in minutes\*mg/dL) during exercise. AOC will be estimated using Trapezoidal Rule.

Analysis will be conducted for glucose levels below range (interstitial glucose  $\leq 70$  mg/dL (3.89 mmol/L), interstitial glucose between 54-70 mg/dL (3 – 3.89 mmol/L),  $<54$  mg/dL (3 mmol/L)) using a contingency table and treatment difference will be calculated using Chi square/Fisher's exact test.

Proportional time (percentage within serious hypoglycemia <54 mg/dL (3 mmol/L)) will be calculated and treatment difference will be calculated using ANOVA/Kruskal–Wallis test, based on whether the data is normally distributed or not respectively.

Insulin utilization as reported by subjects in Outpatient phase and change from baseline will be analyzed using ANOVA.

The Questionnaires will be analyzed using T Test/ANOVA for CRC/outpatient phase. For ANOVA, significant value will lead to a post hoc analysis for identifying the treatment pairs which are significantly different.

Changes from baseline in questionnaire values (numeric) will be analyzed by the ANCOVA model using treatment arm at Outpatient phase, treatment sequence in CRC phase, sex as factors with age, weight and baseline value as covariates.

Example of SAS syntax code that can be used for secondary endpoint analysis is provided in APPENDICES 2.

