#### 4.6.2 APPENDIX 2. Example of SAS syntax code for secondary endpoint analysis.

The following macro can be used for the calculation of area over the curve (AOC):

```
%macro auc (dsn);
  data auctree;
    set &dsn;
    if concentration = 0 and time > tlast then delete;
    x = time;
    y = concentration;
    xpre = lag(x);
    ypre = lag(y);
    xdif = x - xpre;
    if x <= tmax or y = ypre or y =0 or ypre = 0 then do;
      auc = xdif * (( y + ypre ) / 2 );*linear rule;
    end;
    else do;
      auc = xdif * ((y - ypre) / log (y / ypre));
    end;
  run;
```

```

      end;
run;

proc summary data = auctree noprint;
  var auc;
  output out = aucest sum = auCL;
run;

proc sort data = auctree out = part1 nodupkey ;
  by subject ;
run;
data AUCs&i (keep = subject period auCL);
  merge part1 aucest;
run;
%mend auc;

```

The following macro can be used to perform estimation according to Trapezoidal Rule:

```

%macro trap(a,b,n, function);
  data f1;
    do i = 0 to &n ;
      if i = 0 then do;
        x = &a ;
        y = ((&b - &a)/&n )*( &function / 2 );
        output;
      end;
      else if i = &n then do;
        x = &b ;
        y = ((&b - &a)/&n )*( &function / 2 );
        output;
      end;
      else do;
        x = ( &a + i * (( &b - &a) / &n ) );
        y = ((&b - &a) / &n) * &function;
        output;
      end;
    end;
  end;
run;
proc summary data=f1;
  var y;
  output out=p1 sum=areau;run;
proc print data=p1;
run;
%mend;

```

The Chi-Square/Fisher's exact test can be done using the following SAS code example:

```

PROC FREQ DATA = data;
  TABLES param*trt / CHISQ FISHER EXPECTED;

```

```
WEIGHT count;
RUN;
```

Kruskal Wallis test can be performed in SAS using the following reference code:

```
PROC NPAR1WAY DATA=soil WILCOXON;
  CLASS location;
  EXACT WILCOXON / MC;
  VAR claypct;
RUN;
```

T test within the cross over design in CRC phase can be done with the help of the following reference code:

```
PROC TTEST DATA=data PLOTS=interval;
  VAR aval1 aval2 / CROSSOVER = (TrtA TrtB);
RUN;
```

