Table 14.2.3.1.1.1	Summary of Overnight Hypoglycemia at CRC Phase ITT Population
Table 14.2.3.1.1.2	Summary of Overnight Hypoglycemia at CRC Phase PP Population
Table 14.2.3.1.2.1	Summary of Incidence of Overnight Hypoglycemia at CRC Phase ITT Population
Table 14.2.3.1.2.2	Summary of Incidence of Overnight Hypoglycemia at CRC Phase PP Population
Table 14.2.3.2.1.1	Summary of Overnight Hypoglycemia at Outpatient Phase ITT

Number	Title
	Population
Table 14.2.3.2.1.2	Summary of Overnight Hypoglycemia at Outpatient Phase PP Population
Table 14.2.3.2.2.1	Summary of Incidence of Overnight Hypoglycemia at Outpatient Phase ITT Population
Table 14.2.3.2.2.2	Summary of Incidence of Overnight Hypoglycemia at Outpatient Phase PP Population
Table 14.2.3.3.1.1	Summary of Glucose Tablet Usage at CRC Phase ITT Population
Table 14.2.3.3.1.2	Summary of Glucose Tablet Usage at CRC Phase PP Population
Table 14.2.3.3.2.1	Summary of Glucose Tablet Usage at Outpatient Phase ITT Population
Table 14.2.3.3.2.2	Summary of Glucose Tablet Usage at Outpatient Phase PP Population
Table 14.2.3.4.2.1	Summary of Changes in Weight at Outpatient Phase ITT Population
Table 14.2.3.4.2.2	Summary of Changes in Weight at Outpatient Phase PP Population
Table 14.2.3.5.2.1.1	Summary of Exercise Sessions completed at Outpatient Phase ITT Population
Table 14.2.3.5.2.1.2	Summary of Exercise Sessions by subgroup at Outpatient Phase ITT Population
Table 14.2.3.5.2.2.1	Summary of Exercise Sessions completed at Outpatient Phase PP Population
Table 14.2.3.5.2.2.1	Summary of Exercise Sessions by subgroup at Outpatient Phase PP Population
Table 14.2.3.6.2.1	Summary of Number of Minutes Exercised per week at Outpatient Phase ITT Population
Table 14.2.3.6.2.2	Summary of Number of Minutes Exercised per week at Outpatient Phase PP Population
Table 14.2.3.7.2.1	Summary of Number of Calories Burned per Exercise sessions at Outpatient Phase ITT Population
Table 14.2.3.7.2.2	Summary of Number of Calories Burned per Exercise Sessions at Outpatient Phase PP Population
Table 14.2.3.8.2.1	Summary of Number of Steps, Distance achieved During Exercise Sessions at Outpatient Phase ITT Population
Table 14.2.3.8.2.2	Summary of Number of Steps, Distance achieved During Exercise Sessions at Outpatient Phase PP Population
Table 14.2.3.9.1.1	Summary of Mean Carbohydrate Intake at Outpatient Phase ITT Population
Table 14.2.3.9.1.2	Summary of Mean Carbohydrate Intake at Outpatient Phase PP Population

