Table 14.2.3.9.2.1	Summary of Carbohydrate Intake by Hypoglycaemic Events at Outpatient Phase ITT Population
Table 14.2.3.9.2.2	Summary of Carbohydrate Intake by Hypoglycaemic Events at Outpatient Phase PP Population
Table 14.2.3.10.1.1	Summary of Heart Rate at CRC Phase ITT Population

Number	Title
Table 14.2.3.10.1.2	Summary of Heart Rate at CRC Phase PP Population
Table 14.2.3.10.2.1	Summary of Heart Rate at Outpatient Phase ITT Population
Table 14.2.3.10.2.2	Summary of Heart Rate at Outpatient Phase PP Population
Table 14.2.3.11.1.1	Summary of Daily Assessments at CRC Phase ITT Population
Table 14.2.3.11.1.2	Summary of Daily Assessments at CRC Phase PP Population
Table 14.2.3.11.2.1	Summary of Daily Assessments at Outpatient Phase ITT Population
Table 14.2.3.11.2.2	Summary of Daily Assessments at Outpatient Phase PP Population
Table 14.2.3.12.1.1	Summary of HbA1c ITT Population
Table 14.2.3.12.1.2	Summary of HbA1c PP Population
Table 14.2.4.1.1	Analysis of Incidence of Hypoglycemia at CRC Phase ITT Population
Table 14.2.4.1.2	Analysis of Incidence of Hypoglycemia CRC Phase PP Population
Table 14.2.4.1.3	Analysis of Incidence of Hypoglycemia at Outpatient Phase ITT Population
Table 14.2.4.1.4	Analysis of Incidence of Hypoglycemia Outpatient Phase PP Population
Table 14.2.4.2.1	Analysis of Change from baseline in BAPAD-1 score at Outpatient Phase ITT Population
Table 14.2.4.2.2	Analysis of Change from baseline in BAPAD-1 score at Outpatient Phase PP Population
Table 14.2.4.3.1	Analysis of Change from baseline in HFS-II score at Outpatient Phase ITT Population
Table 14.2.4.3.2	Analysis of Change from baseline in HFS-II score at Outpatient Phase PP Population
Table 14.2.4.4.1	Analysis of Change from baseline in HCS score at Outpatient Phase ITT Population
Table 14.2.4.4.2	Analysis of Change from baseline in HCS score at Outpatient Phase PP Population
Table 14.2.4.5.1.1	Analysis of Interstitial Glucose (IG) below Target Range at CRC Phase ITT Population
Table 14.2.4.5.1.2	Analysis of Interstitial Glucose (IG) below Target Range at CRC Phase PP Population
Table 14.2.4.5.2.1	Analysis of Interstitial Glucose (IG) below Target Range at Outpatient Phase ITT Population
Table 14.2.4.5.2.2	Analysis of Interstitial Glucose (IG) below Target Range at Outpatient Phase PP Population
Table 14.2.4.5.3.1	Analysis of Time within Hypoglycemia at CRC Phase ITT Population
Table 14.2.4.5.3.2	Analysis of Time within Hypoglycemia at CRC Phase PP Population

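### The CRC crossover's yes/no outcomes are assigned an unpaired chi-square/Fisher test; an optional ANCOVA and two SAS samples also need correcting

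*SAP*

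**What the plan says.** **Design.** The CRC stage is a two-treatment, two-period crossover (SAP 1.2). SAP 1.3.1: "At the second session, the subject will be crossed over to the other treatment assignment".

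**Overnight hypoglycemia.** SAP 4.3.8: "Incidence of overnight hypoglycemia will be compared for the treatment arms using Chi-Square/Fisher's exact tests at CRC/ Outpatient phase". Exploratory endpoint 4 in SAP 3 confirms that the two CRC treatments are compared, and SAP 5.1 lists "Summary of Incidence of Overnight Hypoglycemia at CRC Phase ITT Population".

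**Interstitial glucose (IG) below range.** SAP 3 defines this secondary endpoint for inpatient and outpatient data. SAP 4.3.7 says it will be analysed "using a contingency table and treatment difference will be calculated using Chi square" or Fisher's exact test, without naming a phase. SAP 5.1 lists "Analysis of Interstitial Glucose (IG) below Target Range at CRC Phase PP Population", with an ITT counterpart.

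**Sample code, Appendix 2.** The code for these tests is "TABLES param*trt / CHISQ FISHER EXPECTED". Continuous CRC data do get a crossover t-test, but no paired method for binary data appears anywhere. A macro is offered for area over the curve (AOC).

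**Optional ANCOVA.** For incidence rates, SAP 4.3.8 allows t-test, ANOVA or ANCOVA. The ANCOVA contains outpatient arm together with a sequence factor built from the CRC and outpatient treatments. The questionnaire ANCOVA in 4.3.7 uses the CRC sequence alone. Appendix 3 gives sample code for the model.

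**The concern.** Chi-square and Fisher treat the two columns of the table as separate people. In the CRC phase they are the same people on two days. The variance that the test uses ignores the within-subject covariance, so its error rate is wrong in a direction set by the sign of the correlation. If a subject prone to lows is prone in both periods (positive correlation), the test is conservative and gives up the power that a crossover is run to obtain. If the correlation is negative, it rejects too often.

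Three smaller faults sit in the same analyses:

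- The ANCOVA in 4.3.8 can leave the arm effect with no degrees of freedom.
- The Appendix 3 sample labels a sum of two means as a comparison.
- The Appendix 2 macro, fed raw CGM values, gives a larger supposed hypoglycemia area to a subject with better glucose.

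**Working it through.** **The plan's own figure.** The documents give no power for any CRC binary comparison. The only sample size is for the outpatient ANOVA (SAP 1.3), and it reproduces: 59/15² = 59/225 = 0.262; with 14 per arm the noncentrality is 3 × 14 × 0.262 = 11.0, and power is 82.3% (79.0% with 13). Then 42 × 1.15 = 48.3, close to the stated 48. None of this changes.

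**1. Unpaired test on paired data.** Inputs: n = 48 and two-sided 0.05 from the SAP. Risks and the correlation ρ are assumptions, because the documents give neither.

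With equal risk p in both periods:

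- variance assumed by chi-square: 2p(1-p)/n
- true variance: 2p(1-p)(1-ρ)/n

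The test therefore rejects at an effective critical value of 1.96/√(1-ρ):

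- ρ = 0.3: 1.96/√0.7 = 2.34, about 1.9%
- ρ = 0.5: 1.96/√0.5 = 2.77, about 0.6%
- ρ = -0.3: 1.96/√1.3 = 1.72, about 8.6%

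Exact enumeration of every four-cell paired table agrees. Joint risk of an event in both periods: pA·pB + ρ√[pA(1-pA)pB(1-pB)].

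Type I error, 30% in both periods (%):

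| ρ | Chi-square | Fisher | McNemar |
|---|---|---|---|
| -0.3 | 9.0 | 5.6 | 5.3 |
| 0 | 5.2 | 2.9 | 5.3 |
| 0.3 | 2.0 | 0.9 | 4.6 |
| 0.5 | 0.6 | 0.2 | 4.3 |

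Exact McNemar holds 2.2 to 3.0%.

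Power, 40% against 20% (%):

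| ρ | Chi-square | McNemar | Fisher | Exact McNemar |
|---|---|---|---|---|
| 0 | 58.6 | 58.0 | 49.0 | 48.0 |
| 0.3 | 59.9 | 72.1 | 48.5 | 63.7 |
| 0.5 | 61.1 | 87.1 | 47.7 | 80.3 |

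The loss is 72.1 - 59.9 = 12.2 points at ρ = 0.3 and 87.1 - 61.1 = 26.0 at ρ = 0.5. For Fisher against exact McNemar it is 15.2 and 32.6.

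Other cases:

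- With 42 subjects, chi-square has 52.4, 52.9 and 53.1% against McNemar's 51.9, 65.0 and 81.9%.
- With the pilot's 5 of 15 on basal reduction (33%, Protocol 4.2) against an assumed 15%, it is 56.5, 57.8 and 58.8% against 56.0, 69.8 and 86.5%.
- For 33% against an assumed 5%, chi-square and McNemar both reach at least 96%. Fisher and exact McNemar are about 94% at ρ = 0. The loss concerns moderate differences.

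**2. ANCOVA in 4.3.8, one record per subject.** Two CRC orders by three arms make six sequence levels. Rank without arm: 1 (intercept) + 5 (sequence) + 1 (sex) + 2 (age, weight) = 9. Adding arm leaves 9, so arm has 0 df, and the arm LS means and A-B are not estimable. With CRC order alone the rank is 1 + 1 + 1 + 2 = 5, and arm raises it to 7 (2 df, A-B estimable).

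**3. Appendix 3 code.**

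- The A versus B contrast has coefficients 1 1 0. On two equal LS means of 10 it returns 10 + 10 = 20, not 0.
- LOWER at 0.025 does not inflate the level, but it looks in one direction only, against the two-sided rule in 4.3.6.
- RANDOM uses SEQ, while CLASS lists trtSEQ.
- Treatment A is placebo in Protocol 2.2 and glucagon in SAP 2.3, and B is the reverse.

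**4. Appendix 2 AOC macro.** It has no threshold and switches to a log rule after tmax. On raw IG over 0 to 300 min:

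| Flat IG (mg/dL) | Macro | Area below 70 | Area below 54 |
|---|---|---|---|
| 100 | 100 × 300 = 30,000 | 0 | 0 |
| 60 | 60 × 300 = 18,000 | 10 × 300 = 3,000 | 0 |
| 50 | 50 × 300 = 15,000 | 20 × 300 = 6,000 | 4 × 300 = 1,200 |

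**The case against.** **Scope.** In words, only one exploratory endpoint gets the unpaired test at the CRC, and its listed outputs are summary tables. For IG below range, 4.3.7 names no phase and the endpoint is time and area, so the CRC tables could be meant for the area analysis. This stands as a limit: that part is an inference. But chi-square/Fisher is the only test named for the below-range contingency table, and nothing exempts the CRC.

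**Unit of analysis.** SAP 2.4 allows several overnight events per night, sets no yes/no rule per subject, and does not say which nights belong to which CRC treatment. This stands, and the rule has to be written before any test can be applied.

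**Size.** Risks and correlations are assumed. The pilot's 33% concerns exercise sessions, not midnight to 6 am. A correlation of 0.5 is near the ceiling for 40% against 20%: (0.20 - 0.08)/√(0.24 × 0.16) = 0.61. Inflation needs a negative correlation, for which there is no evidence; the likelier fault is conservatism. Pairing does not always give a smaller p-value either: the pilot's 5 of 15 against 0 of 15 gives Fisher p = 0.042 and exact McNemar p = 0.0625. All of this is fair. The argument is for a valid test, not a more favourable one.

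**Items 2 to 4.**

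- The ANCOVA is optional, and most exploratory endpoints have their own named test, so few or no planned results depend on it. Appendix 3 has repeated-measures statements; if CRC and outpatient records were stacked by treatment received, rank would rise from 9 to 11. A contrast averaging the sequence cells also stays estimable.
- The SAP takes precedence over the protocol and footnotes its A/B labels.
- Appendix 2 also holds a linear trapezoid macro, and all the code is offered as example.

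These points make items 2 to 4 corrections rather than failures. They do not reach item 1, which is in the SAP text.

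**Conclusion.** The concern holds. As written, the SAP applies an independent-groups test to paired CRC data: explicitly for overnight hypoglycemia, by implication for IG below range. At correlations of 0.3 to 0.5 and moderate differences, the cost is about 12 to 26 points of power (chi-square against McNemar). At zero correlation there is no cost. A negative correlation would raise the false-positive rate, to 9.0% in the case shown. These sizes rest on assumed risks and correlations with one yes/no per subject and period; the mismatch between design and test does not.

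The ANCOVA, contrast and AOC items are real but smaller. The aliasing arises with one record per subject, and the AOC error only if the macro is run on raw CGM values. The questionnaire ANCOVA in 4.3.7 is estimable. The primary ANOVA and its sample size are untouched. The SAP should be corrected before programming.

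**What to change.** 1. **CRC binary outcomes (4.3.7, 4.3.8, Appendix 2).** Define one yes/no per subject and period. For overnight hypoglycemia, the night after each CRC session would fit exploratory objective 5. Compare treatments by McNemar, or by Mainland-Gart to allow for period, and add sample code. Keep multiple instances per night as a descriptive count. Keep chi-square/Fisher, one value per subject, for the outpatient arms.
2. **ANCOVA (4.3.8).** Use the two-level CRC order as the sequence factor, as 4.3.7 already does.
3. **Appendix 3.** Use 1 -1 0, drop LOWER, report two-sided at 0.05, use one name for the sequence variable, and reconcile the A/B labels between Protocol 2.2 and SAP 2.3.
4. **Appendix 2 AOC sample.** Replace it with a linear trapezoid, per subject and session, of max(0, 70 - IG) and max(0, 54 - IG) in mg/dL over 0 to 300 min, with the 54 to 70 band as the sponsor defines it.

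Cost: SAP text and sample code only. No new data, and no change to the primary analysis.
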